8.1.5 Relationship to Study Product

All AEs will have their relationship to study product assessed using the terms: related or not related.

- Related – There is a reasonable possibility that the study product caused the adverse event. Reasonable possibility means that there is evidence to suggest a causal relationship between the study product and the adverse event.
- Not Related – There is not a reasonable possibility that the administration of the study product caused the event.

8.2 ASSESSMENT OF SAFETY EVENTS

AE information collected will include event description, date of onset, assessment of severity and relationship to study product and alternate etiology (if not related to study product), date of resolution (return to baseline or stabilization) of the event, seriousness and outcome. The assessment of severity and relationship to the study product will be done only by those with the training and authority to make a diagnosis and listed on the Form FDA 1572 as the site principal investigator or sub-investigator. AEs occurring during the collection and reporting period will be documented appropriately regardless of relationship. AEs will be followed through resolution (return to baseline or stabilization).

SAEs will be:

- Assessed for severity and relationship to study product and alternate etiology (if not related to study product) by a licensed study physician listed on the Form FDA 1572 as the site principal investigator or sub-investigator.
- Recorded on the appropriate SAE report form, the medical record and captured in the clinical database.
- Followed through resolution by a licensed study physician listed on the Form FDA 1572 as the site principal investigator or sub-investigator.

For timeframe of recording adverse events, please refer to section **6.1**. All serious adverse events recorded from the time of first investigational product administration must be reported to the sponsor with the exception of any listed in section **8.4**.

8.3 REPORTING OF SERIOUS ADVERSE EVENTS

Any AE that meets protocol-defined serious criteria or meets the definition of Adverse Event of Special Interest that require expedited reporting must be submitted immediately (within 24 hours of awareness) to OSRO Safety. Any exceptions to the expedited reporting requirements are found in section **8.4**.

All SAE reporting must include the elements described in section **8.2**.

SAE reports will be submitted via an electronic SAE reporting system (e.g. HiLIT). In the event of system downtime or issues, SAE reports will be submitted using the CCR SAE Report form to the sponsor at: [contact]. CCR SAE report form and instructions can be found at:

<https://nih.sharepoint.com/:u/r/sites/NCI-CCR-OCD-Communications/SitePages/Forms-and-Instructions.aspx?csf=1&web=1&e=uWBX>

Following the assessment of the SAE by OSRO, other supporting documentation of the event may be requested by the OSRO Safety and should be provided as soon as possible.

8.4 WAIVER OF EXPEDITED REPORTING TO CCR

As progression free survival, which includes death due to disease progression is part of the study objectives, and captured as an endpoint in this study, death due to disease progression will not be reported in expedited manner to the sponsor. However, if there is evidence suggesting a causal relationship between the study drug and the event, report the event in an expedited manner according to section **8.3**.

8.5 SAFETY REPORTING CRITERIA TO THE PHARMACEUTICAL COLLABORATORS

Reporting will be per the collaborative agreement.

8.6 REPORTING PREGNANCY

All required pregnancy reports/follow-up to OSRO will be submitted to:

[contact] and to the CCR PI and study coordinator. Forms and instructions can be found here: <https://nih.sharepoint.com/:u/r/sites/NCI-CCR-OCD-Communications/SitePages/Forms-and-Instructions.aspx?csf=1&web=1&e=uWBXtI>

8.6.1 Maternal exposure

If a patient becomes pregnant during the course of the study, the study treatment should be discontinued immediately, and the pregnancy reported to the Sponsor no later than 24 hours of when the Investigator becomes aware of it. The Investigator should notify the Sponsor no later than 24 hours of when the outcome of the pregnancy becomes known.

Pregnancy itself is not regarded as an SAE. However, congenital abnormalities or birth defects and spontaneous miscarriages that meet serious criteria (section **8.1.2**) should be reported as SAEs.

The outcome of all pregnancies should be followed up and documented.

8.6.2 Paternal exposure

Individuals who can father children should refrain from fathering a child or donating sperm during the study and for 28 days after the last dose of lenalidomide and for 3 months after the last dose of CC-486 (5-azacitidine).

Pregnancy of the patient's partner is not considered to be an AE. The outcome of all pregnancies occurring from the date of the first dose until 6 months after the last dose should, if possible, be followed up and documented. Pregnant partners may be offered the opportunity to participate in an institutional pregnancy registry protocol (e.g., the NIH IRP pregnancy registry study) to provide data about the outcome of the pregnancy for safety reporting purposes.

8.7 REGULATORY REPORTING FOR STUDIES CONDUCTED UNDER CCR-SPONSORED IND

Following notification from the investigator, CCR, the IND sponsor, will report any suspected adverse reaction that is both serious and unexpected. CCR will report an AE as a suspected adverse reaction only if there is evidence to suggest a causal relationship between the study product and the adverse event. CCR will notify FDA and all participating investigators (i.e., all investigators to whom the sponsor is providing drug under its INDs or under any investigator's IND) in an IND safety report of potential serious risks from clinical trials or any other source, as soon as possible, in accordance to 21 CFR Part 312.32.

All serious events will be reported to the FDA at least annually in a summary format.

8.8 SPONSOR PROTOCOL DEVIATION REPORTING

A Protocol Deviation is defined as any non-compliance with the clinical trial Protocol, Manual of Operational Procedures (MOP) and other Sponsor approved study related, GCP, or protocol-specific procedural requirements on the part of the participant, the Investigator, or the study site staff inclusive of site personnel performing procedures or providing services in support of the clinical trial.

It is the responsibility of the study Staff to document any protocol deviation identified by the Staff or the site Monitor in the CCR Protocol Deviation Tracking System (PDTs) online application. The entries into the PDTs online application should be timely, complete, and maintained per CCR PDTs user requirements.

In addition, any deviation to the protocol should be documented in the participant's source records and reported to the reviewing IRB per their guidelines. OSRO required protocol deviation reporting is consistent with E6(R2) GCP: Integrated Addendum to ICH E6(R1): 4.5 Compliance with Protocol; 5.18.3 (a), and 5.20 Noncompliance; and ICH E3 16.2.2 Protocol deviations.

9 CLINICAL MONITORING

Clinical site monitoring is conducted to ensure:

- That the rights of the participants are protected;
- that the study is implemented per the approved protocol, Good Clinical Practice and standard operating procedures, and,
- the quality and integrity of study data and data collection methods are maintained.

Monitoring for this study will be performed by NCI CCR Office of Sponsor and Regulatory Oversight (OSRO) Sponsor and Regulatory Oversight Support (SROS) Services contractor. Clinical site monitoring activities will be based on OSRO standards, FDA Guidance E6(R2) Good Clinical Practice: Integrated Addendum to ICH E6(R1) March 2018, and applicable regulatory requirements.

Details of clinical site monitoring will be documented in a Clinical Monitoring Plan (CMP) developed by OSRO. CMPs will be protocol-specific, risk-based and tailored to address human subject protections and integrity of the study data. OSRO will determine the intensity and frequency of monitoring based on several factors, including study type, phase, risk, complexity, expected enrollment rate, and any unique attributes of the study and the site. The Sponsor will conduct a periodic review of the CMP to confirm the plan's continued appropriateness. A change to the protocol, significant or pervasive non-compliance with GCP, or the protocol may trigger CMP updates.

OSRO SROS Monitoring visits and related activities will be conducted throughout the life cycle of each protocol. The first activity is before the study start to conduct a Site Assessment Visit (SAV) (as warranted), followed by a Site Initiation Visit (SIV), Interim Monitoring Visit(s) (IMVs), and a study Close-Out Visit (COV).

Some monitoring activities may be performed remotely, while others will take place at the study site(s). Monitoring visit reports will describe visit activities, observations, findings of protocol non-adherence and associated action items or follow-up required for resolution of findings. Monitoring reports will be distributed to the study PI, NCI CCR QA, coordinating center (if applicable) and the Sponsor regulatory file.

The site Monitor will inform the study team of any deviations observed during monitoring visits. If unresolved, the Monitor will request that the site Staff enter the deviations in the CCR Protocol Deviation Tracking System (PDTs) for deviation reporting to the Sponsor and as applicable per institutional and IRB guidance.

10 STATISTICAL CONSIDERATIONS

10.1 STATISTICAL HYPOTHESIS

- Primary Endpoint(s):
 - Maximum tolerated dose (MTD) of lenalidomide administered orally in combination with romidepsin and CC-486 (5-azacitidine) for up to 6 cycles
 - Frequency (number and percentage) of treatment-emergent AEs
- Secondary Endpoint(s):
 - Overall response rate (including complete response rate and partial response rate), after treatment
 - Duration of response, after treatment
 - Progression-free survival after treatment
 - Event-free survival after treatment
 - Overall survival

10.2 SAMPLE SIZE DETERMINATION

The MTD will be based on the assessment of DLT during the first cycle of treatment and will be defined as the dose level at which less than one-third of patients (0 of 3 or 0-1 of 6 patients) treated experience a DLT, with the next higher dose level demonstrating one-third or a greater number of patients (≥ 2 of 3 or ≥ 2 of 6 patients) having a DLT. If a subject did not experience a DLT and did not finish one cycle of treatment (21 days) they will not be evaluable for determination of the MTD and would be replaced in the dose level. An additional 3 to 6 patients will be enrolled at the MTD, so that a total of 9 patients will be treated at this dose.

Using this dose-escalation scheme the probability of escalating to the next dose level will be based on the true rate of DLT at the current doses given by the following table (each group will be considered independently of the other); Thus, if the true underlying proportion of DLTs is 50% at the current dose there is a 17% probability of escalating to the next dose.

True toxicity at a given dose	10%	20%	30%	40%	50%	60%
Probability of escalating	0.91	0.71	0.49	0.31	0.17	0.08

If all four dose levels are evaluated with 6 patients per dose level and 9 total patients at the MTD, a maximum of 27 evaluable patients will be enrolled. Similarly, if all dose levels are evaluated with 3 patients per dose level and 9 total patients at the MTD, the minimum number of evaluable patients required will be 18. To account of unevaluable patients, accrual ceiling will be set at 36. It is expected that the accrual can be completed in 29 months.

A maximum of 30 patients will be enrolled over 29 months, at a rate of 1-2 patients per month.

After execution of amendment 12/07/2022, we will no longer enroll into the original Arm 2 expansion cohort and will test a new modified dose-expansion arm removing the lenalidomide lead-in window and expanding the cycle length to 28 days to enroll the remaining participants.

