2.5.2 Arms

Number	Name	Description
1	Experimental Treatment: Dose Escalation (Closed: prior amendment 12/07/2022)	Lenalidomide by oral intake at escalating doses of 5, 10, 15, or 20 mg/day on days -7 to 10 of each 21-day cycle (max 6 cycles) with CC-486 (5-azacitidine) at 300mg/day by oral intake on days 1-10, romidepsin at 12mg/m ² by IV infusion on Day 1 and 10 and dexamethasone at 40mg by oral intake on days 1 and 10 of each cycle, to determine MTD
2	Experimental Treatment: Dose Expansion(Closed: with amendment 12/07/2022)	Lenalidomide by oral intake at 20mg on days 1 to 10 of each 28-day cycle (max 6 cycles) with CC-486 (5-azacitidine) at 300mg/day by oral intake on days 1-10, romidepsin at 12mg/m ² by IV infusion on Day 1 and 10 and dexamethasone at 40mg by oral intake on days 1 and 10 of each cycle
3	Experimental Treatment: Dose Expansion	Lenalidomide by oral intake at 20mg (MTD) on days 1 to 10 of each 28-day cycle (max 6 cycles) with CC-486 (5-azacitidine) at 300mg/day by oral intake on days 1-10, romidepsin at 12mg/m ² by IV infusion on Day 1 and 10 and dexamethasone at 40mg by oral intake on days 1 and 10 of each cycle

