3 STUDY IMPLEMENTATION

3.1 STUDY DESIGN

To determine the maximum tolerated dose (MTD), and the safety and toxicity profile of the combination of lenalidomide, CC-486 (5-azacitidine) and romidepsin in patients with refractory/relapsed TCM, a phase 1 open-label, non-randomized, single-center study will be conducted at the NCI. A standard “3 + 3” design will be used to determine the MTD of dose-escalated lenalidomide in combination with fixed doses of CC-486 (5-azacitidine), romidepsin (R) and dexamethasone (D) with an expansion cohort at the MTD.

In patients with relapsed or refractory TCM, lenalidomide will be administered by oral intake in a dose-escalation with a starting dose of 5mg daily, a second dose level of 10mg daily, a third dose level at 15mg daily, and a fourth dose level at 20mg daily on days -7 to day 10 of first cycle (see **Table 1** for additional dose levels and schedules, cycles are 21 days each). After the second cycle, lenalidomide will be given from day 1 to day 10 in each cycle for up to six cycles. CC-486 (5-azacitidine) with a dose of 300mg oral intake daily will be given on day 1 to day 10, romidepsin will be administered at a dose of 12 mg/ m² on days 1 and 10 (±2 days) and dexamethasone will be given on day 1 and 10 (±2 days) of the cycle.

After approval of Amendment 12/07/2022: Participants will receive six cycles (each 28 days in length) of: lenalidomide at the MTD from day 1 to day 10, CC-486 (5-azacitidine) at a dose of 300mg oral intake daily given on day 1 to day 10, romidepsin administered at a dose of 12 mg/ m² on days 1 and 10 (±2 days) and dexamethasone on day 1 and 10 (±2 days) of the cycle.

Treatment will continue for a maximum of 6 cycles or until toxicity (i.e., dose limiting toxicity) as found in Section 3.9 or toxicity requiring discontinuation as defined in Section 3.5) or progressive disease.

The treatment will be repeated for up to 6 cycles. The patients are allowed to proceed to stem cell transplantation (SCT) if eligible during and after the protocol treatment. Patients who undergo SCT before all 6 cycles of protocol treatment are administered will be taken off therapy. All patients who undergo SCT will continue to be followed for survival, but not for toxicity (see Section 3.8)

Cycles 1-6												28
Azacitidine												by mouth once per day
Lenalidomide												by mouth once per day
D												D
R												R

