3.3 DOSE ESCALATION

Dose escalation will proceed according to the following schedule (Table 2). Dose escalation will follow the following guidelines (Table 3). Each patient will continue treatment at the dose level they were enrolled – there will be no intra-patient dose escalation. In case of severe toxicity, the lenalidomide dose should be reduced by one dose level, dose adaption of the other drugs as per investigators discretion.

The MTD is the dose level at which no more than 1 of up to 6 patients experience DLT during the DLT evaluation window(s), or the dose below that at which at least 2 (of ≤ 6) patients have DLT. The protocol will be amended to note the MTD once determined.

NOTE: If enrollment to the current or next higher dose level cannot proceed because a patient at the current dose level is still within the DLT window, screened patients who are in need of urgent treatment may be enrolled at the next lower dose level as long as the ≤ 6 patient limit per dose level is maintained. In the event that these additionally enrolled patients experience DLT(s) after formal evaluation of dose level determinations has taken place, the Principal Investigator will review and assess if any changes to the ongoing protocol/dose escalation or safety parameters need to be considered.

NOTE: After the dose escalation portion was completed, the MTD of lenalidomide was determined to be 20mg.

Table 2: Lenalidomide Dose Escalation Schedule

Dose Level	Lenalidomide
Level -2	0 mg
Level -1	2.5 mg
Level 1	5mg – Starting dose
Level 2	10mg
Level 3	15mg
Level 4	20mg

Table 3: Dose Escalation Guidelines

Number of Patients with DLT at a Given Dose Level	Escalation Decision Rule
0 out of 3	Enter 3 patients at the next dose level.

Number of Patients with DLT at a Given Dose Level	Escalation Decision Rule
≥ 2	Dose escalation will be stopped. This dose level will be declared the maximally administered dose (highest dose administered). Three (3) additional patients will be entered at the next lowest dose level if only 3 patients were treated previously at that dose.

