1 out of 3	Enter at least 3 more patients at this dose level. 
• If 0 of these 3 patients experience DLT, proceed to the next dose level.• If 1 or more of this group suffer DLT, then dose escalation is stopped, and this dose is declared the maximally administered dose. Three (3) additional patients will be entered at the next lowest dose level if only 3 patients were treated previously at that dose.
≤ 1 out of 6 at highest dose level below the maximally administered dose	This is generally the recommended phase 2 dose. At least 6 patients must be entered at the recommended phase 2 dose.

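### Sections 3.3 and 10.2 define the MTD differently; if no lenalidomide level above 20 mg was tested, the declared MTD of 20 mg meets 3.3 but not 10.2

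*Combined protocol and SAP*

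**What the plan says.** Section 10.1 lists as the first primary endpoint "Maximum tolerated dose (MTD) of lenalidomide administered orally in combination with romidepsin" and CC-486.

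Section 3.3 offers two routes to the MTD. One is "The MTD is the dose level at which no more than 1 of up to 6 patients experience DLT" in the evaluation window. The other is "or the dose below that at which at least 2" of up to six patients have one. The two are alternatives, so either is enough.

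Section 10.2 offers one route with two conditions. Fewer than one-third of patients at the level may have a DLT (0 of 3, or 0 to 1 of 6), "with the next higher dose level demonstrating one-third or a greater number of patients" having one (at least 2 of 3, or at least 2 of 6).

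Table 3 in section 3.3 deals with a level that shows at most one DLT in six and lies beneath the level at which escalation stopped. It says of that level: "This is generally the recommended phase 2 dose". The table has no row for a top level that clears.

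On the outcome, section 3.3 records: "After the dose escalation portion was completed, the MTD of lenalidomide was determined to be 20mg". Arm 3 in section 2.5.2 and the last row of Table 1 repeat the MTD label.

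On the range of doses, section 3.1 describes "a third dose level at 15mg daily, and a fourth dose level at 20mg daily", and Arm 1 in section 2.5.2 gives "escalating doses of 5, 10, 15, or 20 mg/day on days -7 to 10". Tables 1 and 2 list nothing above 20 mg, and section 10.2 sizes the study for four levels. Two places disagree: section 1.10.1 names 25 mg as the planned maximum, and section 2.5.1 counts five levels.

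**The concern.** A 3+3 design can end in two ways: a level proves too toxic, or the highest planned level clears. The two definitions agree in the first case and part in the second, and no text says which of them governs.

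The declared dose of 20 mg is the highest level in Tables 1 and 2, so it may be the very case on which the definitions part. To call a dose the MTD in the sense of section 10.2 is to say that a higher dose was given and was not tolerated. To call it the highest level tested says only that escalation ran out of planned levels. Someone choosing a dose for a later study would read these two statements differently, and this is the trial's first primary result.

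**Working it through.** **1. The plan's own figures.** With true DLT rate p, the 3+3 probability of escalating is (1−p)³ + 3p(1−p)² × (1−p)³. At p = 0.5 this is 0.125 + 0.375 × 0.125 = 0.172. For p from 10% to 60% it gives 0.906, 0.709, 0.494, 0.309, 0.172 and 0.082. These match the table in section 10.2 (0.91, 0.71, 0.49, 0.31, 0.17, 0.08), so the arithmetic of that section is sound. The problem is in the definition.

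**2. How many levels the plan assumes.** With L levels and nine patients at the MTD, the maximum is 6(L−1) + 9 and the minimum is 3(L−1) + 9.

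| Levels | Maximum | Minimum |
|---|---|---|
| 4 | 3×6 + 9 = 27 | 3×3 + 9 = 18 |
| 5 | 4×6 + 9 = 33 | 4×3 + 9 = 21 |

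Section 10.2 states 27 and 18, so it is sized for four levels. The escalation cohort of up to 24 in section 2.5.1 is also 4×6 (five levels would need 30), although the same entry says five levels. Section 3.4.1 reports 20 patients enrolled with escalation fully accrued. That number does not discriminate: four levels allow 12 to 24 patients and five allow 15 to 30.

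**3. What can be said about 25 mg.** Section 1.10.1 says that reaching 25 mg would lead to an amendment raising romidepsin to 14 mg/m². Arm 3 still uses 12 mg/m². Nothing therefore indicates that 25 mg was reached and cleared. Two cases remain: no level above 20 mg was opened, or one was opened and was toxic.

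**4. Each definition applied to each case.**

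| Case | Section 3.3 | Section 10.2 |
|---|---|---|
| (a) 20 mg is the top level and clears with at most 1 DLT in 6 | 20 mg, by the first route | No MTD: there is no higher level on which to meet the second condition |
| (b) A level above 20 mg was tested and had at least 2 DLTs | 20 mg | 20 mg |

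Had 20 mg itself failed, both definitions would give a lower dose, so that case does not fit the declaration.

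**5. Was case (a) remote at the design stage?** The documents give no expected DLT rates, so the rates here are assumptions. The chance of reaching level 4 is the product of the escalation probabilities at levels 1 to 3. The chance that level 4 then clears with six patients is (1−p)³[(1−p)³ + 3p(1−p)²] + 3p(1−p)⁵. At 10% for every level this is 0.906³ × 0.886 = 0.66. With rates of 5/10/15/20% by level it is 0.47, with 10/15/20/25% it is 0.28, and with 10/20/30/40% it is 0.07. Unless toxicity was expected to rise steeply, the plan needed a rule for a cleared top level.

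**The case against.** The strongest reply is that section 3.3 is the operating section. Its first route looks written for a tolerated level with no toxic level above it, and the note declaring 20 mg stands in the same section. Section 10.2 could then be read as a restatement of the usual bracketed definition for sizing purposes. The threshold for a toxic level is also the same in both places. This is a plausible account of how 20 mg came to be declared. No text states it, however. The definition that it sets aside is the one in the statistical section, and Table 3 is closer to 10.2 because it ties the recommended dose to a higher level at which escalation stopped.

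A second reply is that the consequence depends on facts that the documents do not give. That stands. The difference in wording is certain, but whether the declared MTD fails section 10.2 is not.

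A third is that only a label is affected. That stands too, and it limits the seriousness of the point.

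A reader might go further in three directions that the documents do not support.

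- One might infer that section 3.3 makes every cleared level an MTD, because its first route omits the word highest. The term itself says maximum, and Table 3 moves enrolment upward after each cleared level, so the intended reading is clear.
- One might infer that 20 mg is unsafe or wrongly chosen. Nothing in the documents suggests either.
- One might infer that removing the lead-in and lengthening the cycle undermines the MTD. Section 1.10.3 discloses that change, and sections 3.2 and 10.3.4 tie DLT assessment to cycle 1. It has no bearing on which definition governs.

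**Conclusion.** The concern holds as an inconsistency in the definition of the first primary endpoint. The two definitions give different answers for a top level that clears, and most of the text indicates that 20 mg was the top level.

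If nothing above 20 mg was tested, the same data read as an MTD of 20 mg under section 3.3 and as no MTD under section 10.2. If a higher level was tested and was toxic, both give 20 mg, and only the stray references to dose levels need correcting. The documents do not settle which case applies.

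The size of the effect is the label on the primary result. The expansion dose, the sample size, the safety assessment and the adverse-event endpoint are unaffected. The point is worth settling before the primary result is reported.

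**What to change.** - Use one definition in sections 3.3 and 10.2: the highest level with at most one DLT in six evaluable patients, called the MTD only if the next higher level met the DLT threshold.
- State whether any level above 20 mg was opened, and give DLT counts by level.
- If a higher level was opened and was toxic, keep the term MTD.
- If none was, replace it in section 2.5.2, Table 1 and section 3.3 with 'MTD not reached; 20 mg is the highest level tested and the recommended expansion dose'.
- Reconcile the 25 mg in section 1.10.1 and the five levels in section 2.5.1 with Tables 1 and 2.

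The cost is wording in those sections and in the report, plus a tabulation of DLT data that the escalation decisions already required. No patient, dose or procedure changes. The drawback is a primary conclusion that may sound less definitive.
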